Before neuraxial placement, all patients have an intravenous catheter placed with automated non-invasive blood pressure, pulse oximetry, and external tocodynamometry monitors applied. All women receive a 500 ml intravenous bolus of crystalloid solution immediately before the initiation of neuraxial analgesia. The epidural space is identified using a 17-gauge Tuohy needle with the patients in the seated position at the estimated L3-4 or L4-5 interspace, via a midline approach using a loss of resistance to saline technique. After identification of the epidural space, a needle-through-needle technique is performed using a 25-G Whitacre needle, placed into the shaft of the previously sited epidural needle to create a single dural puncture. After confirmation of free flow of CSF, initial dosing consists of intrathecal 0.25% bupivacaine 2 mg (0.8 ml) and 10 µg (0.2 ml) fentanyl in the CSE group. Subsequently, the spinal needle is removed and the epidural catheter (19-gauge Duraflex wire-reinforced multiport catheter (Smith Medical, USA)) is advanced 5 cm into the epidural space and secured with the patient in the sitting upright position, using Tegaderm clear occlusive dressing (3M, USA). In the DPE group, after confirmation of free flow of CSF, the spinal needle is withdrawn and the epidural catheter advanced 5 cm into the epidural space. After negative aspiration for blood and CSF, initial dosing consists of 20 ml of 0.1% ropivacaine plus fentanyl 2 µg.ml (premixed) administered in divided doses of 5 ml every 2 min. In both groups, analgesia is maintained using programmed intermittent epidural boluses of 8 ml of ropivacaine 0.1% with fentanyl 2 µg.ml every 45 min starting 30 min after the initial spinal or epidural loading dose, with patient-controlled epidural analgesia (PCEA) of 10 ml, a lockout of 10 min and maximum dose of 50 ml per hour.

If analgesia is inadequate (defined as a patient request for supplemental analgesia beyond self-administered PCEA boluses), an anesthesia provider blinded to group assignment assesses and, if warranted, administers top-up doses according to a predefined algorithm.

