The end time of administration of the loading dose (end of spinal dose injection in the CSE group or epidural medication administration in the DPE group) is designated time 0 ( $t = 0$ ). A blinded investigator collects data at 15 and 30 min and subsequently at 2-h intervals from time zero until delivery. Analgesia is evaluated at all time points using the verbal numeric pain rating scale (NPRS) for the last contraction (0=no pain, 10=worst possible pain). The upper and lower sensory levels are evaluated at 15 and 30 min using temperature discrimination to ice. Motor blockade is assessed at all time points using the modified Bromage score.

The following additional data are recorded every 2 h until delivery: presence of pruritus; nausea; hypotension (defined as systolic blood pressure  $\leq 20\%$  from the patient's admission blood pressure); need for physician top-up; catheter adjustment and catheter replacement. We also assess for the presence of asymmetric blockade, defined as a difference  $> 2$  dermatomal sensory levels between the left and right side as assessed at 15 and 30 min or at any time that sensory levels are checked because of complaints of pain. An obstetrician blinded to group assignments accesses the electronic medical record to review tocometry and continuous fetal monitoring strips and extract uterine contraction and fetal heart rate monitoring patterns in 10-min epochs, for 1 h before and 1 h after the initial spinal (CSE group) or epidural (DPE group) dosing. On the first postpartum day, we assessed for postdural puncture headache and satisfaction with labour analgesia (0-10, 0= very dissatisfied, 10=very satisfied)

The primary outcome of the study is the quality of labour analgesia, which is defined by a composite of five components: asymmetric block after 30 min of initiation (difference in sensory level of more than two dermatomes); epidural top-up interventions; catheter adjustment; catheter replacement; failed conversion to neuraxial anesthesia for cesarean delivery, requiring general anesthesia or replacement of the neuraxial block.

Secondary outcomes include: pain scores; Bromage scores; sensory levels at 15 and 30 min; adverse events (hypotension, nausea, pruritus, postdural puncture headache, fetal heart rate changes); duration of second stage of labor; mode of delivery; total anesthetic dose; PCEA use; and overall satisfaction with analgesia.

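### Is the comparison of total anesthetic dose at risk because the plan does not say whether the loading dose counts?

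*Combined protocol and SAP*

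**What the plan says.** The document has one title and no numbered sections, so places are given by topic.

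- **Secondary outcomes.** The list ends with "total anesthetic dose; PCEA use; and overall satisfaction with analgesia". Total dose is named only there, and nothing defines it.
- **Loading doses (neuraxial procedure).** In the DPE group "initial dosing consists of 20 ml of 0.1% ropivacaine plus fentanyl" at 2 µg/ml. The CSE group receives 2 mg of intrathecal bupivacaine with 10 µg of fentanyl.
- **Maintenance (same paragraph).** Both arms have the same regimen: 8 ml programmed boluses of 0.1% ropivacaine with fentanyl every 45 min, starting 30 min after loading, plus 10 ml PCEA boluses with "a lockout of 10 min and maximum dose of 50 ml per hour".
- **Rescue.** If warranted, a blinded provider "administers top-up doses according to a predefined algorithm"; the drugs and amounts are not given.
- **Time zero (data collection).** It is defined by "The end time of administration of the loading dose". A blinded investigator collects data at 15 and 30 min and "subsequently at 2-h intervals from time zero until delivery".
- **Analysis.** Continuous secondary outcomes get a mean ratio from log-linear regression, and secondary p values are adjusted by the Bonferroni-Holm method.

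**The concern.** Total dose is formally tested, so one would like its definition fixed before the data are seen. The text seems to allow two. The word total suggests that the load counts. A clock that starts when loading ends, with data gathered from then to delivery, suggests that it does not.

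The choice does not affect the arms equally, because the loads differ about tenfold in milligrams while maintenance is identical. With the load in, DPE starts ahead by an amount set by the protocol. With it out, the arms start level. A modest saving in DPE maintenance use could then be reported as lower or as higher consumption from the same data.

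Two smaller gaps sit beside this one. It is not stated whether physician top-ups count. Nor is it stated whether drug given for cesarean anesthesia counts, although part of it could be given before delivery.

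**Working it through.** **Inputs from the plan**
- CSE load: 2.5 mg/ml x 0.8 ml = 2 mg bupivacaine, which agrees with the stated 2 mg; 10 µg fentanyl.
- DPE load: 1 mg/ml x 20 ml = 20 mg ropivacaine; 2 µg/ml x 20 ml = 40 µg fentanyl.
- Programmed bolus: 8 ml x 1 mg/ml = 8 mg ropivacaine.
- PCEA bolus: 10 ml, taken as 10 mg. This assumes the same 0.1% solution, which the plan implies but does not state.

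**Built-in gap with the load counted:** 20 mg (ropivacaine alone) or 20 - 2 = 18 mg (drugs summed).

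**Ratios, DPE to CSE.** Let M be the mean post-loading dose in CSE (mg) and s the amount by which DPE is lower. Top-ups are left out because their content is not given.
- Load out: (M - s)/M, below 1 when s > 0.
- Load in, ropivacaine: (M - s + 20)/M, above 1 when s < 20.
- Load in, drugs summed: (M - s + 20)/(M + 2), above 1 when s < 18.

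The load-out ratio and both load-in ratios therefore disagree in direction when 0 < s < 18 mg, which is less than 1.8 PCEA boluses.

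**Example (M = 100 and s = 10 assumed):** 90/100 = 0.90; 110/100 = 1.10; 110/102 = 1.08.

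**Equal post-loading use (s = 0).** The load-out ratio is 1.00. The plan gives no labour duration, so 4, 6 and 8 h are assumed. Programmed boluses number 5, 8 and 11, giving a lower bound for M of 40, 64 and 88 mg. Adding PCEA at 50 ml/h from time zero gives an upper bound of 240, 364 and 488 mg.

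| Duration | Ropivacaine, load in | Drugs summed, load in |
|---|---|---|
| 4 h | 60/40 = 1.50 to 260/240 = 1.08 | 60/42 = 1.43 to 260/242 = 1.07 |
| 6 h | 84/64 = 1.31 to 384/364 = 1.05 | 84/66 = 1.27 to 384/366 = 1.05 |
| 8 h | 108/88 = 1.23 to 508/488 = 1.04 | 108/90 = 1.20 to 508/490 = 1.04 |

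If the hourly cap covers all pump delivery, the upper bounds are 200, 300 and 400 mg and the lowest ropivacaine ratios are 1.10, 1.07 and 1.05.

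**How often the versions would conflict.** A simulation compared load out with drugs summed. It assumed 50 per arm, a log-scale SD of 0.5 and a true load-out ratio of 0.75 to 0.90. Significance is nominal, before the Holm adjustment.

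| CSE mean M | Opposite point estimates | Exactly one version significant | Opposite and both significant |
|---|---|---|---|
| 60 mg | 85-95% | 90-92% | 2-8% |
| 80 mg | 63-86% | 62-85% | at most 0.05% |
| 100 mg | 38-75% | 42-78% | 0% |

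**Does the text really support leaving the load out?** The time-zero clock governs a blinded investigator's rounds. The items recorded on it are pain score, sensory level, Bromage score, pruritus, nausea, hypotension, need for a top-up, and catheter adjustment or replacement. Drug dose is not one of them. Nor is time zero a general start of data: fetal and contraction tracings are extracted from 1 h before initial dosing, and hypotension is judged against admission blood pressure. The load-out reading therefore borrows a clock written for something else. The plain word total, with PCEA use listed next to it as a separate outcome, points to overall exposure with the load counted.

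**The case for a change.** The strongest case for a change is that this outcome carries an adjusted p value, and that other items, such as asymmetric block, hypotension and the satisfaction scale, are defined while this one is not. Even if total settles the load, it does not settle milligrams or millilitres, ropivacaine alone or summed with intrathecal bupivacaine, fentanyl, top-ups, or cesarean dosing. A modest DPE saving is plausible, because the plan expects the primary composite to fall from 50% to 22.5% and top-ups are one of its components. The simulation also shows that the choice can decide which version reaches nominal significance.

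The missing definition is real and that part stands. The rest carries less weight.

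- No instruction in the plan, followed as written, gives a wrong answer. Either version is a legitimate quantity once labelled.
- The plan nowhere says that total dose measures analgesic need, so counting the load does not contradict a stated purpose.
- The reversal depends on consumption figures that the plan does not give. It disappears if DPE uses more after loading, or saves over 18 mg. With a 10% saving on 248 mg, for example, both versions fall below 1: 0.90 load out, and (223.2 + 20)/(248 + 2) = 0.97 load in.
- Counting top-ups would probably add more drug to CSE and offset some of the gap, so the tabulated ratios illustrate the range and do not estimate a bias.
- A report has to say what it counted. Where the load was given as specified, the other version's means or medians follow by adding or subtracting a constant. The p value cannot be recovered this way, but no main conclusion rests on it.
- Cesarean cases enter the plan through "failed conversion to neuraxial anesthesia for cesarean delivery" in the primary composite. Keeping surgical anesthetic doses out of a labour analgesia total is the obvious reading.

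**Conclusion.** No change is needed. This is a gap that analysts would fill sensibly: count all labour analgesia drug including the load, say so, and describe the result as exposure. Such a total contains a protocol-set DPE excess of 20 mg of ropivacaine, or 18 mg with drugs summed. With equal post-loading use, that alone gives a ropivacaine ratio between 1.50 (4 h, programmed boluses only) and 1.04 (8 h, maximum PCEA). Point estimates reverse between versions only when DPE use after loading is lower by between 0 and 18 mg. Opposite and significant results appeared in at most 8% of simulated trials.

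The 18 and 20 mg gaps come straight from the plan. The ratios rest on assumed durations, a 0.1% PCEA solution and no top-ups; the simulation adds assumed means and spread. One secondary outcome is affected, and neither the primary comparison nor the sample size depends on it.

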**Comparing Effectiveness of CSE Versus DPE for Labor Analgesia**

NCT05068661

3/22/2024

After obtaining written informed consent, parturients are randomised in a 1:1 ratio by computer-generated random sequence to CSE or DPE arms, stratified by parity (nulliparous versus multiparous) and class of obesity (BMI <40 vs. 40-50 kg.m^-2). Allocation is concealed in sequentially numbered opaque envelopes. Patients, obstetricians, nurses, and anesthesia providers involved in follow-up of labour analgesia and data collection are blinded to group allocation. The anesthesia provider placing the neuraxial block and the supervising attending anesthesiologist are not involved in data collection or in follow up of labour analgesia.

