Based on the study by Chau et al a sample size of 50 patients per group had an 80% power at alpha 0.05 to detect a reduction in the composite primary outcome from 50% in the CSE group to 22.5 % in the DPE group. To account for dropouts, we aim to enrol up to 60 patients per group to have complete data on 100 subjects.

Descriptive statistics for patient characteristics and outcomes are calculated and reported as median (IQR [range]) or number (proportion) as appropriate. The primary composite outcome is compared between exposure groups using a chi-squared test and an effect size is reported as a risk ratio. Secondary outcomes are assessed using chi-squared or Fisher exact tests as appropriate, with associated risk ratios for categorical measures and univariate log-linear regression with mean ratios for continuous measures. All p values for the secondary outcomes are adjusted for multiple comparisons using the Bonferroni-Holm method to control family-wise error rate and adjusted p values are reported. Only p values and adjusted p values < 0.05 are considered statistically significant. Analysis is performed using R version 4.3.1, with the power calculation performed using NQuery.

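### Does the stated 80% power at 50 per group fail because the plan does not say whether the chi-squared test is continuity-corrected?

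*Combined protocol and SAP*

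**What the plan says.** The document has no numbered sections; the relevant text is in its closing paragraphs on sample size and statistical analysis.

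- **Sample size.** The power claim is "a sample size of 50 patients per group had an 80% power at alpha 0.05 to detect a reduction in the composite primary outcome", the fall being "from 50% in the CSE group to 22.5 % in the DPE group". Up to 60 per group are enrolled to allow for dropouts, "to have complete data on 100 subjects".
- **Allocation.** The opening paragraph has patients "randomised in a 1:1 ratio by computer-generated random sequence".
- **Primary analysis.** "The primary composite outcome is compared between exposure groups using a chi-squared test", with a risk ratio as the effect size.
- **Software.** "Analysis is performed using R version 4.3.1, with the power calculation performed using NQuery".

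Nothing says whether the chi-squared statistic carries a continuity correction, whether alpha is one- or two-sided, or which R function or option is used.

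**The concern.** A reader who recomputes the sample size does not land on 50 per group and 80% together. The Pearson test needs fewer patients for that power and the continuity-corrected test needs more, so at 50 per group one form is above the stated figure and the other below it.

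The analysis is to be run in R, whose base function for a two-by-two table applies the continuity correction unless told otherwise. An analyst who accepted that default would be running the form that falls short of the claimed power.

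The choice could also matter to the result. Significance is judged at 0.05, and near that boundary the two forms can give opposite answers from the same data. If the form were settled only after unblinding, the primary conclusion could in principle depend on the choice.

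**Working it through.** **Inputs.** From the document: p1 = 0.50, p2 = 0.225, 1:1 allocation, alpha 0.05, power 80%, 50 complete patients per group. Assumed: a two-sided test, so z = 1.960 for alpha and 0.842 for power. Derived: difference d = 0.275; mean risk = (0.50 + 0.225)/2 = 0.3625.

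**Step 1: sample size for the Pearson test.**

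n = [1.960 × √(2 × 0.3625 × 0.6375) + 0.842 × √(0.50 × 0.50 + 0.225 × 0.775)]² / d²

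- First term: 1.960 × √0.4622 = 1.960 × 0.6798 = 1.332
- Second term: 0.842 × √0.4244 = 0.842 × 0.6514 = 0.548
- n = (1.332 + 0.548)² / 0.0756 = 46.8, so 47 per group

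**Step 2: sample size with the continuity correction.**

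n_c = (n/4) × [1 + √(1 + 4/(n × d))]² = (46.8/4) × [1 + √1.311]² = 53.8, so 54 per group

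**Step 3: approximate power at 50 per group.**

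- Pearson: (0.275 × √50 − 1.332)/0.6514 = 0.94, giving 82.6%.
- Corrected (d reduced by 1/50 = 0.02): (0.255 × √50 − 1.332)/0.6514 = 0.72, giving 76.5%.

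**Step 4: exact check.** Summing binomial probabilities over every possible pair of event counts gives:

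| Quantity | Pearson | Continuity-corrected |
|---|---|---|
| Power, 47 per group | 80.3% | 73.0% |
| Power, 50 per group | 82.8% | 77.1% |
| Power, 53 per group | 85.7% | 80.5% |
| Power, 60 per group | 89.1% | 84.7% |
| True type I error, 50 per group, both risks 36.25% | 5.0% | 3.1% |

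The corrected test first passes 80% at 53 per group by enumeration (79.4% at 52), against 54 by formula.

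**Step 5: other routes to the plan's figure.** At 50 per group, Fisher's exact test has 77.1% power, the unpooled-variance formula gives 84.7% and the arcsine formula 82.9%. A one-sided 0.05 level gives about 90% uncorrected and 85% corrected. None returns 80% at exactly 50. The simplest account is that 47 was rounded up to 50 and the design target was quoted in place of the attained power; the document does not confirm this.

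**Step 6: how often the two forms disagree.** Under the planning rates with 50 per group, Pearson is significant and the corrected form is not in 82.8% − 77.1% = 5.7% of trials. The reverse never happens. For example, with 23/50 against 13/50 events:

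- Pearson: 0.20² / (2 × 0.36 × 0.64/50) = 4.34, p = 0.037
- Corrected: (0.20 − 0.02)² / (2 × 0.36 × 0.64/50) = 3.52, p = 0.061

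**Step 7: scale.** Keep the Pearson test at 50 per group and move one planning rate. A DPE rate of 24% in place of 22.5% lowers exact power from 82.8% to 78.0%. A CSE rate of 48% in place of 50% lowers it to 77.1%, the same figure as the corrected test has under the original rates.

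**The case for a change.** The strongest case for a change is that the primary test should leave the analyst no choice, and here two analysts could each follow the text faithfully and run different tests. At 50 per group, every 10-event difference from 21 against 11 to 29 against 19 is significant by Pearson and not significant once corrected. The patients enrolled beyond 50 per group cannot be counted on to rescue the power, because they are reserved for dropouts. One sentence would close the matter.

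Part of this stands. The form of the test is not written down, and the two forms do part company near the boundary. The rest does not carry:

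- An unqualified chi-squared test is most naturally read as the Pearson test, and that test delivers the promised power. The shortfall appears only once a software default is brought in from outside the document, and naming R commits the trial to no particular option.
- Nothing in the document suggests that the power was computed for a different test from the one to be used in the analysis.
- The 3.1% type I error is not a separate harm. The correction errs on the cautious side, and its cost is the same power loss seen from another angle.

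**Conclusion.** No change follows. On the plain reading, 50 complete patients per group give about 83% power for 50% against 22.5%, so the stated 80% is met and slightly understated. If the corrected form were used, power would be about 77%, roughly 3 points below the claim. That shortfall equals the effect of a two-point error in the assumed CSE rate, which is well within the uncertainty of any planning rate. The test would remain valid, with a true type I error near 3%.

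This is missing detail that an analyst can fill sensibly by using the uncorrected two-sided test. Quoting 83% in place of 80% would change neither the enrolment target nor any result.

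The conclusion rests on a two-sided 0.05 level, which the document does not state, and on exactly 50 analysed patients per group. If all 60 per group were analysed, both forms would exceed 80%, at 89% and 85%.

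### Randomisation is stratified by parity and obesity class, but no planned analysis uses either factor, which gives up some precision if they predict the outcome

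*Combined protocol and SAP*

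**What the plan says.** The opening paragraph of the combined protocol and SAP, on randomisation and blinding, says that "parturients are randomised in a 1:1 ratio by computer-generated random sequence to CSE or DPE arms" and that this is "stratified by parity (nulliparous versus multiparous) and class of obesity" (BMI below 40 versus 40-50). Two binary factors give four strata. No block size or other balancing method is mentioned.

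The last paragraph, on statistical analysis, sets out every planned comparison:

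- Primary outcome: "The primary composite outcome is compared between exposure groups using a chi-squared test and an effect size is reported as a risk ratio".
- Categorical secondary outcomes: "Secondary outcomes are assessed using chi-squared or Fisher exact tests as appropriate, with associated risk ratios for categorical measures".
- Continuous secondary outcomes: "univariate log-linear regression with mean ratios for continuous measures".

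Neither parity nor obesity class appears in any of these, and univariate makes the omission explicit for the continuous outcomes. No subgroup or sensitivity analysis uses the factors, and no reason is given for leaving them out. The secondary outcomes include "duration of second stage of labor; mode of delivery; total anesthetic dose".

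**The concern.** Stratifying the randomisation suggests that the sponsor thought these factors might predict outcome. An analysis that ignores them treats the differences between strata as random noise.

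Two things follow if the strata are prognostic. First, the crude comparison is less precise than a stratified one. Second, if allocation is also blocked within strata, the arms are balanced by design on part of the variation that the crude variance still counts. The crude standard error is then too large and the test rejects less often than 5% under the null.

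Validity is not at stake. What may be lost is some power on the composite, and possibly more precision on secondary outcomes that depend on parity. Precision is scarcer there because all secondary p values are adjusted by Bonferroni-Holm.

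**Working it through.** **The plan's own figure.** Inputs from the sample size paragraph: 50% versus 22.5%, alpha 0.05, 80% power, 50 per group. Sidedness is not stated, so two-sided is assumed.

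Pooled-variance formula: n = [1.960 × √(2 p̄(1-p̄)) + 0.842 × √(p1 q1 + p2 q2)]² / (p1 - p2)².

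- p̄ = (0.50 + 0.225)/2 = 0.3625, so 2 p̄(1-p̄) = 0.4622, with square root 0.6798.
- p1 q1 + p2 q2 = 0.2500 + 0.1744 = 0.4244, with square root 0.6514.
- n = (1.3325 + 0.5483)² / 0.275² = 3.537/0.0756 = 46.8, so 47 per group.

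At 50 per group the formula gives 82.6% power, and exact enumeration of the uncorrected chi-squared test gives 82.8%. The stated 50 is therefore slightly generous for the planned test.

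**The two tests compared.**

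- Crude: z = (p̂1 - p̂0) / √[p̄(1-p̄)(1/n1 + 1/n0)].
- CMH: z = Σ(a_k - n1k m_k/N_k) / √[Σ n1k n0k m_k(N_k - m_k) / (N_k²(N_k - 1))]. In stratum k, a_k is the number of events in one arm, n1k and n0k are the arm sizes, m_k is all events and N_k is all women.

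With exact 1:1 balance in every stratum, the Mantel-Haenszel risk ratio equals the crude one, so only the variance differs.

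**Simulation.** The following are assumptions, because the documents do not give them:

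- strata shares of 35/15/35/15% (half nulliparous, 30% with BMI 40-50);
- a logistic outcome model with the odds ratios shown;
- marginal rates of 50% versus 22.5% for power, and 36.25% in both arms for type I error.

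There were 100 women per trial and 400,000 trials per cell. Both tests were uncorrected, two-sided at 5%.

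| Odds ratio, parity/BMI class | Type I error, crude vs CMH (blocks of 4) | Power, crude vs CMH (blocks of 4) | Gain, blocks of 4 | Gain, simple randomisation |
|---|---|---|---|---|
| 1/1 | 5.2 vs 5.1% | 83.3 vs 83.0% | -0.3 | -1.6 |
| 2/1.5 | 4.7 vs 4.9% | 83.7 vs 84.0% | +0.3 | -0.4 |
| 3/2 | 4.3 vs 5.0% | 84.2 vs 85.7% | +1.5 | +1.4 |
| 4/3 | 3.6 vs 4.9% | 84.8 vs 87.6% | +2.8 | +3.4 |

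Gains are in percentage points of power. With simple randomisation within strata, crude type I error is about 5.2% throughout. With blocks of 4, the crude standard error of the log risk ratio is 0, 1, 3 and 5% larger than the Mantel-Haenszel one in the four rows.

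A separate simulation fixed 18/7/18/7 women per arm in the strata, with equal odds ratios for both factors and 40,000 trials per scenario. It points the same way: gains of 0, 0.3, 1.0, 2.6 and 3.8 points at odds ratios of 1, 1.5, 2, 3 and 4, with crude type I error down to 3.1%.

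**Sparse strata.** With shares of 45/5/45/5%, each small stratum holds about 5% × 100 = 5 women. CMH type I error stays at 4.9-5.1%. Its gain is 0.9-1.2 points at 3/2 and 2.2-2.5 points at 4/3.

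**Second-stage duration.** Suppose log duration is modelled linearly and parity explains a share R² of its variance. The unadjusted standard error is then larger by the factor 1/√(1-R²). For R² of 0.1, 0.2 and 0.3 (an assumed range) this is 1.054, 1.118 and 1.195. Precision is proportional to 1-R², so the effect equals losing 10, 20 or 30% of the women who reach a second stage.

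**The case against.** The strongest reply is that the planned test is valid, simple, slightly conservative at worst, and keeps more than the stated 80% power in every scenario. The design target is met without any change. All of that stands, and it limits how much weight the point can carry.

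The sign of the benefit is also uncertain. It depends on whether allocation is blocked and on how strongly the strata predict the composite, and the documents give neither. With simple randomisation and weak prediction, CMH loses 0.4 to 1.6 points. Gains of 1.4 points or more in the main simulation need odds ratios of 3/2 or above, which nothing in the documents supports for a composite of block asymmetry, top-ups, catheter problems and failed conversion. This also stands. Still, the possible loss is small, and the possible gain is about twice as large (3.4 against 1.6 points).

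The second-stage figures come from assumed R² values and a linear model of log duration. If the plan's log-linear regression means a log-link model, the formula does not apply directly. They illustrate a range and are not evidence about this trial.

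Finally, the document is dated 3/22/2024 and does not say whether outcome data were already in hand. If they were, replacing the primary test would be a post hoc change. That bears on how the change is made, not on whether the plan should address the strata.

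**Conclusion.** The concern holds. Two factors define the randomisation, neither enters any analysis, and no reason is offered. The cost is efficiency only, and only if the factors are prognostic. On the primary composite it is about one point of power or less when each odds ratio is 2 or below, rising to roughly 3 to 4 points at the strongest associations tried. If allocation is blocked, the crude test is also conservative, with type I error as low as 3.6% with blocks of 4 and 3.1% with exact balance. The loss may be larger for secondary outcomes that parity predicts. These sizes rest on assumed strata shares and odds ratios, and on assumed R² for second-stage duration. The change is worth making because it is cheap, but the trial does not depend on it.

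**What to change.** - **Primary outcome:** use a CMH test stratified by parity and BMI class, comparing women by assigned group, without continuity correction. Report a Mantel-Haenszel risk ratio with its 95% confidence interval. Keep the crude chi-squared test as a sensitivity analysis.
- **Continuous secondary outcomes:** add both factors as covariates in the log-linear models.
- **Categorical secondary outcomes:** use CMH with a Mantel-Haenszel risk ratio when all expected counts in the collapsed table are at least 5. Keep Fisher's exact test for rarer events such as postdural puncture headache, accepting that those comparisons remain unstratified.
- **Randomisation:** state whether allocation was blocked within strata.
- **Timing:** if outcome data by arm have already been seen, keep the crude test as primary, add the stratified analysis as a labelled sensitivity analysis, and give the reason for the unadjusted choice.

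A separate wording point: say that the primary test is uncorrected. Exact power at 50 per group is 82.8% uncorrected but 77.1% with a continuity correction, against the stated 80%.

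The cost is SAP wording and a few lines of R. Both factors must be known in order to randomise, so no new data or patients are needed. The known downside is a loss of about 0.3 points of power (blocks of 4) to 1.6 points (simple randomisation) if the strata turn out not to be prognostic.

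### The two planned methods for secondary outcomes leave sensory level and Bromage score without an interpretable effect measure (minor, secondary outcomes only)

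*Combined protocol and SAP*

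**What the plan says.** The combined protocol and SAP has no numbered sections, so places are named by paragraph.

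- **Outcome assessment.** On block height the text reads: "The upper and lower sensory levels are evaluated at 15 and 30 min using temperature discrimination to ice". On motor block, the grades of which are not listed, it reads: "Motor blockade is assessed at all time points using the modified Bromage score".
- **Outcome definitions.** Both measures are secondary outcomes: "Secondary outcomes include: pain scores; Bromage scores; sensory levels at 15 and 30 min". The same part defines one component of the primary composite as "asymmetric block after 30 min of initiation (difference in sensory level of more than two dermatomes", that is, as a difference in dermatomes.
- **Statistical analysis.** The tests are given first: "Secondary outcomes are assessed using chi-squared or Fisher exact tests as appropriate". The effect measures, and the model for continuous outcomes, come in the same sentence: "with associated risk ratios for categorical measures and univariate log-linear regression with mean ratios for continuous measures". All secondary p values are then adjusted by Bonferroni-Holm.

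The plan does not say which route sensory level or Bromage score takes. It gives no numbering for dermatomes or Bromage grades, no cut-off for block height or motor block, and no rank or ordinal method. The two-dermatome threshold defines left-right asymmetry, not block height.

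**The concern.** The plan sorts secondary outcomes into categorical and continuous. Sensory level and Bromage grade are ordered scales and fit neither label as they stand.

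- **As continuous measures**, they would be summarised by a mean ratio. That needs a scale with a true zero, and dermatome numbers have none. The size of the ratio, and whether it lies above or below 1, then follows from an unstated numbering. A Bromage ratio likewise depends on the value given to no block.
- **As categorical measures**, a single risk ratio requires a binary outcome, hence a cut-off, and none is given.

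At stake is whether a reader can interpret the reported comparison of block height and motor block between the two techniques. With no coding or cut-off fixed, it could also be chosen after the data are seen.

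**Working it through.** **Plan's own figure.** The plan gives no figure on this point. Its only power statement concerns the primary composite (50% v 22.5%, 50 per group). Using the normal approximation, (0.275×√50 − 1.96×√(2×0.3625×0.6375)) / √(0.5×0.5 + 0.225×0.775) = 0.94, so power is 82.6%. That agrees with at least 80% and is not touched by what follows.

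**Inputs.** From the plan: 50 per group. Assumed, because the plan gives none: dermatome SD 2 (range 1.5 to 3), shifts of one or two dermatomes, the Bromage distributions, and two-sided alpha 0.05 without Holm adjustment.

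**1. Mean ratio for sensory level.** Take group means at T8 and T10. Let m1 be the coded T8 mean and m2 the coded T10 mean. The ratio is m1/m2 and z = ln(m1/m2) / √[(SD²/50)(1/m1² + 1/m2²)], with SD²/50 = 0.08.

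| Numbering | m1 (T8) | m2 (T10) | Ratio | z | Difference |
|---|---|---|---|---|---|
| Upward from S5 = 1 | 15 | 13 | 1.15 | 4.97 | 2 |
| Upward from L5 = 1 | 10 | 8 | 1.25 | 4.93 | 2 |
| Upward from L1 = 1 | 6 | 4 | 1.50 | 4.77 | 2 |
| Thoracic number | 8 | 10 | 0.80 | −4.93 | −2 |

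The ratio changes with the origin, and its direction changes with the direction of counting. |z| stays between 4.8 and 5.0. The difference is two dermatomes in every row; only its sign follows the direction of counting.

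**2. Mean ratio for Bromage.** Assume no block and the next two grades at 90/8/2% v 80/15/5%.

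- No block coded 0: means 0.08 + 2×0.02 = 0.12 and 0.15 + 2×0.05 = 0.25; ratio 2.08, z = 1.35, p = 0.18.
- No block coded 1: means 1.12 and 1.25; ratio 1.12, z = 1.42, p = 0.16.
- Any block v none: 20%/10% = 2.0 under either numbering.

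If the log-linear model means regression on log-transformed scores, it also fails at a score of 0. The plan does not say which model is meant.

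**3. Cut-off for sensory level.** Assume normal means T10 v T9, SD 2, rounded to whole dermatomes. The risk ratio is 89.4%/77.3% = 1.16 for T11 or higher, 59.9%/40.1% = 1.49 for T9 or higher, and 10.6%/4.0% = 2.64 for T6 or higher.

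**4. Power, simulated at 50 per arm.**

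| Sensory level | Chi-squared, all levels | Fisher, all levels | Wilcoxon | Log-link mean ratio |
|---|---|---|---|---|
| Shift 1, SD 1.5 | 49% | 55% | 89% | not run |
| Shift 1, SD 2 | 20–23% | 28% | 66–68% | about 70% |
| Shift 1, SD 3 | 7% | 11% | 36% | not run |
| Shift 2, SD 2 | 86–89% | 92% | over 99% | not run |

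The loss arises only when all levels are tested as unordered categories. For Bromage at 90/8/2% v 80/15/5%, chi-squared on any block has about 31% power and Wilcoxon about 29%. At 85/10/5% v 65/22/13%, both have about 65%.

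**The case against.** The strongest reply has four parts.

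**Power.** A reader might infer that the plan will test every dermatome level as a separate category and so usually miss a real one-dermatome difference. The documents do not support that. The categorical route is tied to risk ratios, and a table of about 11 levels yields no single risk ratio, so this is the least natural reading, although it is not excluded. On the continuous route there is no loss (about 70% against 66–68% for Wilcoxon). For Bromage, chi-squared on any block does as well as Wilcoxon. This stands.

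**Multiplicity.** The power figures use unadjusted 0.05, while the plan applies Bonferroni-Holm. At the strictest Holm step with an assumed 15 tests, a one-dermatome shift at SD 2 has about 29% power by Wilcoxon and 34% by the log-link model. A rank test would therefore often miss it too. This also stands, and power is not the reason for the change.

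**Presentation, not inference.** The p value barely depends on the numbering, and the plan's medians with IQR and range show group levels on the original scale. That lessens the risk of misreading. But a descriptive summary is not a between-group effect with an interval, and the mean ratio is the effect measure the plan provides for continuous outcomes.

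**Flexibility.** The plan's wording about appropriateness might be read as leaving room for ordinal methods. In the sentence on secondary tests it governs only the choice between chi-squared and Fisher.

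**Conclusion.** The point holds as a minor one. The plan's two routes do not give sensory level an interpretable effect: one two-dermatome contrast can be reported as anything from 0.80 to 1.50 under four ordinary numberings. This is arithmetic once the group means are placed at T8 and T10; the near-constant |z| rests on the assumed SD of 2. For Bromage, the spread from 2.08 to 1.12 rests on an assumed grade distribution, but the dependence on the zero point does not.

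The power comparison of about 20% against 68% applies only if all levels are tested as unordered categories, with a one-dermatome shift, SD 2 and unadjusted alpha 0.05. It should not be read as the expected performance of the plan. Nor does anything here show that the planned tests are invalid or that the primary result is at risk: the primary chi-squared test, its risk ratio and the sample size are unaffected.

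**What to change.** In the statistical analysis paragraph:

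1. Compare upper and lower sensory level at 15 and 30 min by Wilcoxon rank-sum test, with a Hodges-Lehmann difference in dermatomes and its 95% CI. This matches the way the plan already expresses asymmetric block.
2. Analyse Bromage as any motor block versus none, by chi-squared or Fisher exact test with a risk ratio, so that the p value and the effect size describe the same quantity. State the grade numbering and the time point or summary used, for example any block at any assessment. A Hodges-Lehmann shift would not help here: at 90/8/2% v 80/15/5%, 0.9×0.8 + 0.08×0.15 + 0.02×0.05 = 73% of between-arm pairs are tied, and the estimated shift would be 0.
3. Keep log-linear mean ratios for positive continuous outcomes such as second-stage duration and total dose.
4. Keep Bonferroni-Holm over all secondary tests.

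The cost is a few sentences of text and a few lines of R, with no new data. The downsides are that secondary effects appear on more than one scale and that dichotomising Bromage discards grade detail, which the descriptive tables can still show.
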